#### 4. OUTPUT PLANNED FOR THE STUDY REPORT (BLINDED PHASE)

#### 4.1 **Tables to be Included in Study Report**

In the following sections, the different results are presented in the order in which it is planned to make them appear in the study report.

The table templates are available in the Appendix of the SAP. The content shown in the templates are an example only. It is not based on real study data or details concerning design.

#### 4.1.1 Summary of subject information

- 1. Table [TDS01a] Subject Disposition (Blinded Phase) All Subjects
- 2. Table [TDM01a] Summary of Demographics (Blinded Phase) ITT Population
- 3. Table [TMH01a] Summary of General Medical History ITT Population
- 4. Table [TMH02a] Summary of Breast Cancer Medical History ITT Population
- 5. Table [TMH03a] Summary of Menstrual History ITT Population

- 6. Table [TCM01a] Summary of Prior Medications and Treatments (Blinded Phase) ITT Population
- 7. Table [TCM02a] Summary of Concomitant Medications and Treatments (Blinded Phase) ITT Population
- 8. Table [TSD01a] Summary of Study Drug Compliance by Visit (Blinded Phase) ITT Population

# 4.1.2 Summary of safety endpoints

- 9. Table [TAE01a] Summary of Adverse Events (Blinded Phase) Safety Population
- 10. Table [TAE02a] Number (%) of Subjects with Adverse Events by Body System and Preferred Term (Blinded Phase) – Safety Population
- 11. Table [TAE03a] Number (%) of Subjects with Serious Adverse Events by Body System and Preferred Term (Blinded Phase) Safety Population
- 12. Table [TAE04a] Number (%) of Subjects with Severe Adverse Events by Body System and Preferred Term (Blinded Phase) Safety Population
- 13. Table [TAE05a] Number (%) of Subjects with Study Agent Related Adverse Events by Body System and Preferred Term (Blinded Phase) Safety Population
- 14. Table [TAE06a] Number (%) of Subjects with Adverse Events by Preferred Term and Overall Frequency (Blinded Phase) Safety Population
- 15. Table [TVS01a] Summary of Vital Signs and Change from Baseline (Blinded Phase) Safety Population
- 16. Table [TPE01a] Summary of Physical Examination (Blinded Phase) Safety Population
- 17. Table [TLB01a] Summary of Laboratory (Hematology) Test Results Safety Population
- 18. Table [TLB02a] Summary of Laboratory (Blood Chemistry) Test Results Safety Population
- 19. Table [TLB03a] Summary of Urine Pregnancy Test Results (Blinded Phase) Safety Population

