# 1.3 Change in Study Conduct

The study was early terminated. Following careful consideration and review of the development program for BHR700 (4-Hydroxytamoxifen Gel, 4-OHT), it was determined that breast density reduction may not be the optimal surrogate marker to support drug development for a target indication of the reduction of the risk of breast cancer.

Planned analyses will be conducted using data available in the clinical database. The sample size of the study may no longer be powered due to the lower number of subjects and shorter duration of treatment for a large proportion of subjects due to the early termination of the study. Therefore, the

interpretation of the analysis results will be cautious. Moreover, the emphasis of the statistical analysis will be on descriptive statistics, rather than hypothesis testing.

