# 3. STATISTICAL METHODS

#### 3.1 General

All data will be analyzed using the Statistical Analysis System (SAS®; Version 9.2 or higher).

Safety and efficacy data will be summarized and presented by treatment group and time point in summary tables. Continuous variables will be presented by descriptive statistics: n, mean, standard deviation, median, minimum, and maximum. Categorical variables will be tabulated by frequency count and percentage.

When the actual treatment received by a subject is different from the randomized treatment assigned, the subject will be analyzed per the randomized treatment for the efficacy parameters (using the ITT population); while the subject will be analyzed per actual treatment that was taken for the safety parameters (using the safety population).

Where appropriate, all statistical tests will be two-sided hypothesis tests performed at the 5% level of significance for main effects and all confidence intervals will be two-sided 95% confidence intervals.

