#### Adverse Events

- All adverse events (AE) will be summarized with MedDRA primary system organ class (SOC) and preferred term.
- Summary tables of severe AEs, SAEs and study drug related AEs will also be provided.
- Listings of all AE, serious adverse events (SAE), and severe AEs will be provided.

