#### 3.8 Change to Planned Protocol Analysis

Since the study was early terminated, many subjects did not have visit of End of Blinded Phase at week 52. The current nominal Visit of "Week 52" will include both "Week 52" and "End of Study" (EOS). No imputation will be done for the missing data.

Since the study was terminated early, a brief clinical study report will be planned for this study and will focus on the safety and PK/PD results, where PK/PD results of blind phase will be reported only. The baseline characters, safety data and PK/PD data will be reported in the study report.

However, mammographic efficacy data may be analyzed appropriately as ad-hoc analyses after carefully reviewed data. The results of ad-hoc analyses will be reported separately.

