# 5.1.2 Summary of safety endpoints

29. Table [TAE01b] Summary of Adverse Events (Open-Label Phase) – Safety Population

- 30. Table [TAE02b] Number (%) of Subjects with Adverse Events by Body System and Preferred Term (Open-Label Phase) Safety Population
- 31. Table [TAE03b] Number (%) of Subjects with Serious Adverse Events by Body System and Preferred Term (Open-Label Phase) Safety Population
- 32. Table [TAE04b] Number (%) of Subjects with Severe Adverse Events by Body System and Preferred Term (Open-Label Phase) Safety Population
- 33. Table [TAE05b] Number (%) of Subjects with Study Agent Related Adverse Events by Body System and Preferred Term (Open-Label Phase) Safety Population
- 34. Table [TAE06b] Number (%) of Subjects with Adverse Events by Preferred Term and Overall Frequency (Open-Label Phase) Safety Population
- 35. Table [TVS01b] Summary of Vital Signs and Change from Baseline (Open-Label Phase) Safety Population
- 36. Table [TPE01b] Summary of Physical Examination (Open-Label Phase) Safety Population
- 37. Table [TLB01b] Summary of Laboratory (Hematology) Test Results (Open-Label Phase) Safety Population
- 38. Table [TLB02b] Summary of Laboratory (Blood Chemistry) Test Results (Open-Label Phase) Safety Population
- 39. Table [TLB03b] Summary of Urine Pregnancy Test Results (Open-Label Phase) Safety Population

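### The AE tables by term give only percentages of dosed women, and no listed output reports exposure, although early termination shortened treatment for many

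*SAP*

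**What the plan says.** SAP 1.3 (Change in Study Conduct) reports "shorter duration of treatment for a large proportion of subjects due to the early termination of the study". SAP 3.8 adds that "many subjects did not have visit of End of Blinded Phase at week 52" and that "a brief clinical study report will be planned for this study and will focus on the safety and PK/PD results". SAP 3.3.2 plans no efficacy analysis for that report, so safety is its main content along with PK/PD.

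For adverse events, SAP 3.3.1 says "All adverse events (AE) will be summarized with MedDRA primary system organ class (SOC) and preferred term", and SAP 3.1 sets the general rule: "Categorical variables will be tabulated by frequency count and percentage". The denominator (SAP 2.1) is every woman with at least one dose, however long she was followed. In SAP 4.1.2, tables TAE02a to TAE06a are all counts and percentages of women; TAE02a is titled "Number (%) of Subjects with Adverse Events by Body System and Preferred Term (Blinded Phase". SAP 5.1.2 repeats the set for the open-label phase, for example "Number (%) of Subjects with Adverse Events by Body System and Preferred Term (Open-Label Phase".

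The lists in SAP 4.1, 4.2, 5.1 and 5.2 name no table or listing of treatment duration, subject-years or time to event. The nearest outputs are subject disposition, a listing of discontinued women, and study drug compliance. Protocol section 3.0 (Secondary Objectives) frames safety and tolerability over 52 weeks of application.

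**The concern.** When women are followed for very different lengths of time, a percentage of women with an event depends on both the event rate and the follow-up. Without the follow-up, a reader cannot separate the two. The natural reference is the protocol's 52 weeks, and many women did not get there.

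Two features make a misreading easier. SAP 3.8 folds end-of-study assessments into the nominal Week 52 visit, so by-visit safety data from women stopped early will carry a 52-week label. The caution in SAP 1.3 does mention shorter treatment, but as a reason for lost power; it does not say how long anyone was treated.

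The stakes lie mainly in events that appear late or accumulate. The protocol synopsis singles out uterine, cardiovascular and thromboembolic events and hot flushes for special attention. The study dose of 8 mg/day is above the 0.25 to 4 mg/day that protocol 2.2 lists as given before, so this report would be an early source of longer-term safety data at that dose.

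**Working it through.** **Is there a figure to reproduce?** No. The documents give no AE incidence, no number of women stopped early and no follow-up times. The sizes below are illustrations under stated assumptions.

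**Does any planned output already show exposure?** Compliance is the nearest candidate. SAP 3.7 defines it per visit as grams used, divided by 3.52 g times the days between visits, and takes the overall figure as the average over visits. Duration cancels: a fully compliant woman treated for 13 weeks and one treated for 52 weeks both score about 100%. It is also set to missing when any canister is not returned (SAP 3.2), and the open-label phase has a compliance listing but no summary table. Disposition counts women, not time. By-visit counts in other tables would show roughly who reached Weeks 13, 26 and 39, but the Week 52 count mixes in end-of-study visits.

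**Direction.** Let F(t) be the probability of a first event by week t. The expected crude percentage is the average of F(Tᵢ) over women, where Tᵢ is follow-up capped at 52 weeks. F cannot decrease, so this average cannot exceed F(52). It equals F(52) only if no first event would have come after a woman's cut-off.

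**Size.** Assume a share f stops at week s, the rest complete 52 weeks, and the hazard is constant. With 52-week incidence I:

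crude = (1 − f) × I + f × [1 − (1 − I)^(s/52)]

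For I = 30%, 1 − 0.70^(26/52) = 16.3% and 1 − 0.70^(13/52) = 8.5%.

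| Share stopped early | Stop at week 26 | Stop at week 13 |
|---|---|---|
| 25% | 0.75 × 30 + 0.25 × 16.3 = 26.6% | 0.75 × 30 + 0.25 × 8.5 = 24.6% |
| 50% | 0.50 × 30 + 0.50 × 16.3 = 23.2% | 0.50 × 30 + 0.50 × 8.5 = 19.3% |
| 100% | 16.3% | 8.5% |

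**Sensitivity to timing.** Take half the women stopping at week 26. If every first onset falls before week 26, the table still shows 30%. If every first onset falls after week 26, it shows 0.50 × 30 + 0.50 × 0 = 15%. The constant-hazard 23% lies between.

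**Between arms.** Take 52-week incidences of 20% and 10%, with half of each arm stopping at week 26.
- Higher arm: 0.50 × 20 + 0.50 × (1 − √0.80) × 100 = 15.3%.
- Lower arm: 0.50 × 10 + 0.50 × (1 − √0.90) × 100 = 7.6%.
- The ratio is 2.02 against a true 2.0. The difference is 7.7 points against a true 10.

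**What a rate would show.** Under the same assumption, 30% over 52 weeks is −ln(0.70) = 0.357, or 35.7 first events per 100 subject-years (taking 52 weeks as a year), whatever the stopping pattern.

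**The case against.** The strongest case on the other side has five parts.

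- **The SAP never calls these percentages 52-week incidence.** They are correct proportions of dosed women, the truncation is disclosed, and the plan promises cautious interpretation. This stands: the fault is a missing context figure, not a wrong number.
- **Not every AE table can be checked.** TAE01a and TAE01b are titled only as summaries of adverse events, and the shells are not available. This stands, so the point is confined to TAE02 to TAE06. No listed title or method text mentions exposure.
- **A constant hazard fits early-onset events poorly.** Protocol 2.2 cites a DCIS study of 6 to 10 weeks in which half the gel group had hot flushes. The population and dose differed, but events with that timing would be largely captured before most cut-offs. This stands and limits the concern to late or cumulative events.
- **Truncation may be mild.** Open-label tables are planned, and entry required completing the blinded phase (SAP 1.2), which suggests that some women had full exposure. This is fair, and is why the table above includes mild cases.
- **Both arms were cut short.** A reader might infer that the report makes the gel look safer than placebo-controlled data should show. The documents do not support that. Termination was a decision about the whole study, similar follow-up by arm leaves the ratio almost unchanged, and nothing indicates unequal stopping. Only the absolute difference shrinks.

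None of this supplies the missing exposure information.

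**Conclusion.** The point holds in a limited form. The report's main content will be safety, follow-up was cut short for a large share of women, and the planned outputs do not tell a reader how long anyone was treated. The AE percentages are sound as observed proportions but cannot answer the protocol's 52-week safety objective.

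The size is unknown. If the hazard is constant, a 30% event would show as about 27%, 23% or 16% when a quarter, half or all of the women stop at week 26, and lower if they stop sooner. Early-onset events would be close to their 52-week figure; late ones would fall furthest below it.

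A reader might go further and say that the report understates harm or biases the comparison. The documents do not support either: the SAP makes no 52-week claim for the percentages, and the arm ratio is largely preserved if follow-up is similar by arm. This is a cheap improvement that should be made, not an error that invalidates the tables.

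**What to change.** 1. Add to SAP 4.1 and 5.1 a table of weeks on study gel and total subject-years, by randomised arm and phase.
2. For all TEAEs, SAEs, related AEs and the protocol's special-attention events, add first events per 100 subject-years at risk, with 95% CIs. State when time at risk starts and ends in each phase.
3. Footnote TAE02 to TAE06 in both phases to say that percentages are over variable follow-up and are not 52-week incidence.

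No new data are needed. The first dose is given under supervision on Day 1 (protocol 7.2), the stop date and total drug used go on the CRF (protocol 5.4), and AE onset is collected (protocol 8.1).

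The cost is a few extra tables and their programming. Subject-year rates assume a roughly constant hazard, so they need care for events that cluster early or late. A Kaplan-Meier estimate at week 52 is optional. It assumes that stopping is uninformative, and it should show numbers at risk because few women may reach week 52.

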# 4.1.3 Summary of PK/PD endpoints

- 20. Table [THR01a] Summary of Hormones Results (Blinded Phase) ITT Population
- 21. Table [TBB01a] Summary of Bone Biomarker Results (Blinded Phase) ITT Population
- 22. Table [TCP01a] Summary of Coagulation Parameters Results (Blinded Phase) ITT Population
- 23. Table [TPK01a] Summary of Plasma Concentration Results (Blinded Phase) ITT Population
- 24. Table [TEM01a] Summary of Endometrial Change (Blinded Phase) ITT Population (Only if data available)

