	15. Women with a concurrent illness, disease or condition that, in the
	opinion of the Investigator, would limit their compliance with
	study requirements or place them at additional risk.

Test Product, Dose, and Mode of Administration:	The BHR-700 gel formulation contains 2 mg/mL 4-OH tamoxifen (0.2%) in a clear, colorless, absorptive hydro-alcoholic gel base formulated to provide continuous release of 4-OH tamoxifen. The BHR-700 gel is supplied in a non-aerosol canister with a 1 mL fixed-dose pump.
	Two (2) fixed unit doses of BHR-700 gel will be applied daily to each breast. Each actuation dispenses 1 mL of gel. A total of 8 mg/day (4 mg/breast) of 4-OHT will be administered daily, unless dose reduction by the Investigator, is deemed necessary for reasons of tolerability.
	The placebo gel is identical in appearance and consistency to the BHR-700 gel.
	Treatment compliance will be monitored by the Investigator staff who will check subject diaries and weigh the IP canister(s) when dispensed and upon return.
Duration of Treatment:	Up to 52 weeks for primary efficacy assessment with an optional and additional 52 weeks of open-label treatment of BHR-700 gel.
Criteria for Evaluation	
Efficacy Measures:	Mammograms will be centrally analyzed. The reader will be blinded as to the treatment group (BHR-700 gel or placebo) and time point of each subject. Cumulus 2D will be the primary endpoint method with Volpara 3D as a secondary endpoint method.
Safety Measures:	
 
Safety assessments will include evaluation of all AEs/serious adverse events (SAEs), with special attention given to uterine abnormalities, cardiovascular events, and thromboembolic events. Additional important safety parameters specific for this indication are: 
 
Endometrial changes
 
Breast evaluation
 
Coagulation factors
 
Bone biomarkers
 
Changes in menstrual cycle; unexpected vaginal bleeding
 
 
 

	To address these safety parameters, subjects will undergo the following assessments:
	A bilateral mammogram with both the raw and processed 2D image DICOM files needs to be performed within 3 months prior to randomization. The same (make/model/serial number) mammography machine must be used for the Week 52 mammogram, and if the subject is participating in the Open-Label phase, the Week 104 mammogram. If the mammogram is older than 3 months but less than 18 months, or it cannot be provided in the format required for

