## 9.6 Study Populations

Three analysis populations will be defined and analyzed:

- 1. Intent-to-treat (ITT) population will contain all subjects who are randomized into the study. All efficacy parameters will be analyzed using the ITT population. In the case of a subject who was randomized but did not take the study drug, the analysis will be done for this subject using the randomized treatment.
- 2. Per-protocol population will contain all ITT subjects who do not have any major protocol deviation. The major protocol deviations will be described in the SAP and identified by BHR PHARMA, LLC before the database is locked.
- 3. Safety population will contain all subjects who receive at least one dose of study drug. All safety parameters will be analyzed using safety population.

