# 2. ELABORATION OF STUDY PROTOCOL

#### 2.1 Study Populations

Three analysis populations will be defined and analyzed:

- 1. Intent-to-treat (ITT) population will contain all subjects who are randomized into the study. All efficacy parameters will be analyzed using the ITT population. In the case of a subject who was randomized but did not take the study drug, the analysis will be performed for this subject using the randomized treatment.
- 2. Per-protocol (PP) population will contain all ITT subjects who completed Week 52 assessments and do not have any major protocol deviation. The major protocol deviations will be identified by BH Ireland before the database is locked and unblinded.
- 3. Safety population will contain all subjects who receive at least one dose of study drug. All safety parameters will be analyzed using safety population.

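### The coagulation, bone biomarker and endometrial tables are labelled ITT, although both documents send safety parameters to the safety population, as treated

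*SAP*

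**What the plan says.** The protocol synopsis (1.3), under Safety Measures, opens a list with "Additional important safety parameters specific for this indication are". The list includes "Endometrial changes", "Coagulation factors" and "Bone biomarkers".

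Protocol 9.6 then sets the population: "All safety parameters will be analyzed using safety population". Protocol 9.8 adds that safety results are grouped by the treatment the woman really had.

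The SAP keeps both rules. SAP 2.1 repeats the population rule and defines the set: "Safety population will contain all subjects who receive at least one dose of study drug". SAP 3.1 assigns efficacy parameters in the ITT population as randomised, and continues: "while the subject will be analyzed per actual treatment that was taken for the safety parameters (using the safety population").

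SAP 3.6 places bone biomarkers and coagulation parameters under a PD/PK heading, to be summarised by visit and treatment group. It does not say whether that group is the randomised or the actual one, and it does not mention endometrial change. SAP 4.1.3 lists "Table [TCP01a] Summary of Coagulation Parameters Results (Blinded Phase) ITT Population" and labels TBB01a (bone biomarkers) and TEM01a (endometrial change, only if data exist) ITT as well. In SAP 4.1.2 the tables for AEs, vital signs, physical examination, haematology, chemistry and pregnancy tests all carry the safety population.

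**The concern.** Three measures that the protocol singles out as safety parameters are tabulated in a population that the SAP otherwise pairs with efficacy and randomised assignment. Coagulation shares its pre-dose, Week 26 and Week 52 visits with haematology and chemistry (Protocol Appendix 1). If a woman had been supplied with the wrong gel, her haematology would be shown under the gel she used, while her coagulation result from the same visit could be shown under the gel she was assigned. A woman randomised but never dosed could add to the baseline rows of these three tables and to no others in the safety set.

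This matters more than usual because SAP 3.3.2 plans no efficacy analysis for the report and SAP 3.8 says the report will focus on safety and PK/PD results. These tables are among its main outputs.

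**Working it through.** There is no planned figure to reproduce. The check sets the texts side by side and then sizes the consequence.

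1. **Classification.** Protocol 1.3, Safety Measures, names endometrial changes, coagulation factors and bone biomarkers. Protocol 8.5, inside the safety assessment chapter, also lists coagulation factors and bone biomarkers among the laboratory tests.
2. **Rule.** Protocol 9.6 and 9.8 and SAP 2.1 and 3.1 agree: safety parameters use the safety population, by actual treatment.
3. **Application.** SAP 4.1.2 follows the rule. SAP 4.1.3 labels TCP01a, TBB01a and TEM01a ITT.
4. **Declared change?** SAP 3.8, the section for departures from the planned analysis, covers the pooling of Week 52 with the end-of-study visit, the absence of imputation, the brief report and ad hoc efficacy work. It does not say that these measures stop being safety parameters or move to ITT.
5. **Who is affected.** By SAP 3.7 the safety population is a subset of ITT. The two sets differ only by women randomised but never dosed. The two groupings differ only for women whose gel was not the one assigned. Neither count is in the documents.
6. **Size for a mean.** Let D be the true drug effect, n the number of placebo women with data at a visit, and m the number of them who in fact used active gel and showed the full effect. Grouped as randomised, the placebo mean shifts by (m/n) × D, and the observed difference is (1 − m/n) × D.
   - Planned placebo arm: 330 × 1/3 = 110. With m = 1 the shift is 1/110 = 0.9% of D. With m = 5 it is 5/110 = 4.5%.
   - The trial stopped early and the numbers per visit are not given. Assuming n = 30 to 90, m = 1 gives 1/30 = 3.3% down to 1/90 = 1.1% of D.
   - With m = 0 there is no shift.
7. **Size for a rare finding.** One endometrial finding in a misplaced woman would turn 0/30 into 1/30 = 3.3% on placebo, with n = 30 again assumed. This needs a supply error and a finding in the same woman.

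**The case against.** The best defence is that the SAP follows a scheme. Section 3.3.1 sets out what it treats as safety analysis (AEs, haematology and chemistry, vital signs and physical examination, pregnancy tests), and 3.6 treats bone, hormone, coagulation and plasma data as PD/PK. Protocol 9.1 lets the SAP prevail over the protocol's statistical section. On this view there is only a missing sentence in 3.8.

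That defence holds in part, because the gap is largely one of classification and documentation. But the precedence clause settles SAP against protocol section 9. It cannot settle SAP 2.1 and 3.1 against SAP 4.1.3, and the synopsis list lies outside section 9. Endometrial change appears in neither 3.3.1 nor 3.6, so the scheme does not cover it.

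Four stronger readings are tempting, and the documents do not carry them.

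- *The SAP plans to count these measures by randomised arm.* A reader may infer this, since it is the only assignment rule tied to ITT. But 3.6 says only treatment group, and the as-randomised rule in 3.1 is written for efficacy parameters. The text is ambiguous; it does not state such a plan.
- *The hormone (THR01a) and plasma concentration (TPK01a) tables break the same rule.* The synopsis list names neither, and the synopsis puts plasma levels under a separate pharmacokinetic heading.
- *The matching listings are wrong too.* SAP 4.2.2 lists haematology, chemistry, vital signs and physical examination on ITT as well. That is the SAP's convention for listings, and an ITT listing loses nobody.
- *The labels hide harm.* Grouping as randomised would dilute a real effect, but no supply error is reported. Kits are allocated by a web-based system (Protocol 6.4), and randomisation and the supervised first dose are both described for Day 1 (Protocol 7.2), so few women should be undosed. Individual coagulation, bone and endometrial listings are also planned.

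**Conclusion.** The point stands for three tables. The ITT label on TCP01a, TBB01a and TEM01a contradicts the protocol's classification of these measures and the SAP's own population rule, and no declared change explains it. What follows is that results could be inconsistent between tables of the same report. A biased safety conclusion has not been shown.

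The numerical effect is probably small: about 1.1% to 3.3% of the drug effect per misplaced placebo woman, resting on an assumed 30 to 90 placebo women per visit and on that woman showing the full effect. If nobody was wrongly supplied or left undosed, no figure in the tables changes. The change is still worth making because it costs almost nothing and keeps one woman's results from one visit under one arm.

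**What to change.** - In SAP 4.1.3, change the population of TCP01a, TBB01a and TEM01a from ITT to the safety population, grouped by actual treatment.
- In SAP 3.6, state that coagulation factors, bone biomarkers and endometrial change follow the safety rule in 3.1. This also gives endometrial change a place in the methods text.
- Gel is dispensed every 13 weeks, so a supply error could affect one interval only. One sentence in SAP 3.1 should say how actual treatment is assigned in that case; the AE tables need it equally.
- Leave the ITT listings as they are. Applying the same rule to THR01a and TPK01a is sensible, since a plasma level describes the gel applied, but optional.

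The cost is a population flag and a title in three tables and two sentences of text, with no new data. If the sponsor prefers to keep ITT, the minimum is to declare and justify the reclassification in SAP 3.8 and to state which treatment grouping applies.
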